13.5. Expedited Reporting of Related Unexpected SAEs

If an SAE is identified as being related and unexpected by the Chief Investigator it will be reported by ICR-CTSU to the main REC, the Sponsor and all other interested parties within 15 days of being notified of the event.

The Principal Investigators at all actively recruiting sites will be informed of any related unexpected SAEs occurring within the trial at appropriate intervals.

13.6. Follow up of Serious Adverse Events

SAEs should be followed up until clinical recovery is complete or until disease has stabilised. SAE outcomes should be reported to ICR-CTSU using the relevant section of the SAE form as soon as the Principal Investigator or designee becomes aware of the outcome.

13.7. Annual Safety Reporting

An annual progress report will be provided to the main REC by ICR-CTSU and copied to the Sponsor at the end of the reporting year. This will include data about related unexpected SAEs and whether any safety concerns have arisen during the reporting period.

13.8. Reporting Pregnancies

If any trial participant becomes pregnant while receiving trial treatment or up to 90 days after receiving trial treatment, this should be reported to ICR-CTSU using the pregnancy reporting form. Participants who become pregnant should discontinue from trial treatment immediately. Pregnancies should be followed up until conclusion and all follow-up information should be reported to ICR-CTSU. If the outcome of the pregnancy meets the definition of serious (i.e. congenital abnormality) this should be reported to ICR-CTSU following the serious adverse event reporting procedures described above.

Adverse event observed in trial participant Responsibilities of Participating Centre Adverse event considered serious as No defined by the trial protocol? IMMEDIATE REPORTING No immediate reporting COMPLETE TRIAL SPECIFIC SAE FORM* required - record on relevant CRF Submit form to ICR-CTSU within 24 hours of becoming aware of the event Sites must respond immediately to Receipt of SAE acknowledged by ICR-CTSU personnel requests for further information for CI and any missing / unclear data queried review/Roche reporting ICR-CTSU forward SAE to the Chief Investigator (CI) or nominated representative for assessment of relatedness and expectedness. Report is returned to the Responsibilities of Sponsor as per Agreement ICR-CTSU once assessment is complete. Both the PI and CI PI and/or CI suspects SAE is related suspect SAE is unrelated CI (or nominated No further reporting representative) required assessment of Related unexpected SAEs will be expectedness of the reported SAR by ICR-CTSU to: • Main REC within 15 calendar days of **Expected** Unexpected initial report Sponsor institution Related unexpected • Principal investigators at regular SAE SAR intervals Requires expedited ICR-CTSU report all SARs reporting

Figure 1: Flow diagram for SAE reporting, and action following report

All SAEs should be followed up until resolution.

to Main REC annually. Sponsor institution also notified at agreed

timelines

Related unexpected SAEs Follow Up

Additional relevant information reported to Main REC and Sponsor as soon as possible

14. STATISTICAL CONSIDERATIONS

14.1. Statistical Design and Sample Size Justification

Sample size justification for co-primary outcomes

The sample size requirements are driven by the co-primary outcome of patient-reported 2-year breast symptoms, hence this is considered first. A total of 192 patients (96 in each randomised group) would provide 92% power to exclude a 2-year mean breast symptoms subscale score (from EORTC QLQ-BR23) at least 10 points higher for PBT compared with tailored RT (assuming standard deviation (SD) =19 and 1-sided α =0.025 as testing for non-inferiority). Non-inferiority of PBT will be concluded if the upper 95% confidence limit for the difference between mean breast symptoms scores is <10. The sample size allows for 10% unevaluable for patient-reported outcome at 2 years, from experience with previous breast RT trials. A 10-point difference is usually considered a minimally important difference for EORTC quality of life scores.

A sample size of 192 patients provides ~99% power to detect a difference in mean heart dose of at least 1 Gy between PBT and tailored RT (assuming SD =1 Gy and 2-sided α =0.05); 1 Gy reduction in mean heart dose for PBT corresponds to an estimated 7.4% reduction in rate of major coronary events(10). The effect of PBT versus tailored RT should be shown for both co-primary outcomes in order to establish clinical benefit; the conjunctive power for this overall assessment is 91% (100 x 0.92 x 0.99).

Sample size justification for mechanistic outcomes

Sample size calculations for the mechanistic study are primarily based on validating published findings suggesting end of range RBE>1.1(41). This study compared pre- to post-treatment radiological lung changes in Hounsfield Units (HU) per Gray (HU/Gy) (RBE) between PBT and photons (N=10 in each group), with estimated mean difference of -1.08 (for PBT vs RT) and SD =1.1 (standardised effect size 0.98). Compared with Underwood's retrospective study, PARABLE's harmonised, prospective imaging will provide a far improved methodology for detecting post-treatment HU changes, hence it is possible that anticipated effect sizes in PARABLE may be larger than those in Underwood's study. Allowing for 10% unevaluable at 2 years, 96 patients per group (192 total) provides 90% power to detect standardised effect sizes >0.5 (mean difference >0.55 HU/Gy, SD 1.1) in terms of radiological lung changes from pre- to post-treatment, comparing PBT and tailored RT (2-sided α =0.05).

Sample size justification for the other mechanistic hypotheses is as follows:

96 patients in the PBT group will provide >90% power to detect standardised effect sizes >0.4 in terms of mean differences in radiological changes in lung and ribcage(39) between each of the 3 alternative RBE models versus 1.1 RBE model (PBT patients only). This assumes use of a paired t-test with 2-sided α =0.017 to account for the 3 pairwise comparisons, and allows for 10% unevaluable at 2 years.

A total of 192 patients (96 per group) provides 94% power to test non-inferiority of PBT compared with RT in terms of relative difference between planned and accumulated mean heart dose assuming 9% for tailored RT and aiming to exclude >10% for PBT, allowing for 10% unevaluable at 2 years (SD = 2% and 1-sided α =0.05).

14.2. Treatment Allocation

Patients will be allocated to PBT (in Manchester or London) versus tailored RT at local centre in a 1:1 ratio. Treatment allocation will use a minimisation algorithm with a random element, to ensure balanced distributions of clinically important factors (balancing factors) between treatment groups. Balancing factors will include IMN RT (yes/no), randomising centre, type of surgery (breast conserving surgery with axillary surgery / mastectomy with axillary surgery / axillary surgery only), breast reconstruction (none/autologous/non-autologous), and need for tumour bed boost.

14.3. Endpoint Definitions

14.3.1. Co-Primary endpoints

- Mean heart dose from treatment plan (PBT or VMAT)
- Patient-reported normal tissue toxicity in the breast (EORTC QLQ-BR23 breast symptoms score) at 2 years

Mean heart dose is a predictor for late major coronary events, with an estimated increase in risk of major coronary events in patients irradiated for breast cancer of 7.4% per Gray mean dose to the whole heart and no evidence of a threshold below which there is no risk.

The EORTC QLQ-BR23 is a validated quality of life tool widely used in breast cancer patients across disease stages and treatment modalities, comprising 4 symptom scales (breast symptoms, arm symptoms, systemic therapy side effects, upset by hair loss) and 4 functional scales (body image, sexual functioning, sexual enjoyment, future perspective). Each scale ranges from 0-100, with higher scores indicating worse symptoms and better functioning respectively. The breast symptoms scale is a composite score encompassing breast pain, breast swelling, breast oversensitivity and skin problems on affected breast. Previous breast RT trials have shown 2-year toxicity to be a good marker for late toxicity, with relative differences between RT treatments changing little after 2 years although absolute rates increase for many years following RT.

14.3.2. Secondary endpoints

14.3.2.1 Dose to organs at risk and normal tissues

Mean lung and contralateral breast doses measured from the treatment plan (PBT or VMAT) will be reported.

14.3.2.2 Early toxicity and health-related quality of life

Early skin and oesophageal toxicity assessed by clinician-recorded CTCAE v 5.0 weekly on treatment, 2 weeks post-RT then weekly until acute reaction graded as 0 (none) or 1 (mild). Severe toxicity is defined as grade 3 or worse.

Patient-assessed early toxicity including skin, breast pain and swelling, fatigue, insomnia, cough and breathlessness, sore mouth/throat will be assessed using items from the PRO-CTCAE, EORTC QLQ-C30 and QLQ-BR23. Health-related quality of life will be assessed using items from the EORTC QLQ-C30 including cognitive functioning, emotional functioning, sexual functioning and social functioning. PRO

for early toxicity and health-related quality of life will be collected weekly on treatment and then weekly until week 12.

Scores from the EORTC questionnaires will be calculated according to established guidelines. The proportion of patients with moderate/marked effects for individual items from the questionnaires will be calculated. PRO-CTCAE has separate endpoints for each toxicity measuring severity of symptoms and interference with usual or daily activities, and uses the CTCAE grading scale, with severe effects defined as grade 3 or worse.

14.3.2.3 Late toxicity and health-related quality of life

Cough and breathlessness will be assessed by clinician-recorded RTOG at 3, 6 and 12 months. RTOG uses a similar scale to CTCAE, ranging from 0 (no symptoms) to 5 (death directly related to radiation effects); severe effects are defined as grade 3 or worse.

Late toxicity and health-related quality of life will be assessed by patients using PRO including EORTC QLQ-C30, QLQ-BR23, Body Image Scale and items capturing breast changes resulting from cancer treatments (established in previous trials). Questionnaires will be administered at baseline, 6, 12, 24, 60 months. Scores for the EORTC questionnaires and Body Image Scale will be calculated according to the relevant scoring manuals. The proportion of patients with moderate/marked effects for individual items from the questionnaires will be calculated.

Skin, breast / chest wall / reconstructed breast, rib and shoulder late toxicity will be assessed by clinicians using methodology established in previous trials at annual follow-up to 5 years. Effects are scored on a 4-point scale (none, mild, moderate, marked). The proportion of patients with moderate/marked effects for individual endpoints will be calculated.

The incidence of major cardiac events will be reported, defined as proportion of patients with atherosclerotic coronary heart disease or other heart disease death, myocardial infarction, coronary revascularisation, or hospitalisation for major cardiovascular event (heart failure, valvular disease, arrhythmia, or unstable angina). International Classification of Diseases (10th revision, I-20 to I-25 and I-30 to I-152)

14.3.2.4 Health economic consequences

Analysis will utilise the Healthcare resource use questionnaire developed for the trial and the EuroQol five-dimensional questionnaire (EQ-5D-5L). These will be collected at baseline, 3, 6, 12, 24 and 60 months.

14.3.2.5 Receipt of allocated intervention, delays and re-planning

The number and proportion of patients receiving their allocated intervention (at least one fraction of photon RT or PBT) will be considered for each trial arm, along with reasons, as a means of assessing acceptability of PBT to patients. The proportion of patients with a delay to photon RT or PBT exceeding 4 weeks' overall treatment time, and the proportion requiring re-planning will be presented.

14.3.2.6 Cancer disease outcomes

Incidence of second primary cancers (including contralateral breast, lung and oesophagus) will be defined as proportion of patients.

Loco-regional tumour control is defined as time from randomisation to loco-regional recurrence i.e. recurrence (or new primary) in ipsilateral breast or regional lymph nodes. Patients will be censored at time of death prior to loco-regional recurrence. Location of loco-regional tumour recurrence will also be of interest.

Disease-free survival is defined as time from randomisation to any recurrence (local, regional or distant), contralateral breast cancer or death from breast cancer. Patients will be censored at time of non-breast cancer death prior to recurrence or contralateral breast cancer.

Overall survival is defined as time from randomisation to death from any cause.

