5.3. Inclusion Criteria

- 1) Age ≥18 years, female or male
- 2) Histologically proven invasive breast carcinoma treated with:
 - a) Breast conservation surgery with axillary surgery (biopsy or dissection)

OR

b) Mastectomy with axillary surgery (biopsy or dissection)

OR

- c) In the case of an occult breast primary, axillary surgery (biopsy or dissection) only is permissible
- 3) Recommended to undergo RT to the breast/chest wall +/- axilla +/- IMN

- 4) Estimated lifetime risk of radiation-induced late cardiac toxicity around 2% or higher*
 - * Calculated from tables of mean heart dose, age and cardiovascular risk factors (pre-existing cardiac disease, other circulatory diseases, diabetes, chronic obstructive pulmonary disease, smoking, body mass index >30 kg/m²)(10).
 - N.B. Mean heart dose is estimated using wide-tangent field placement in deep inspiration breath hold (DIBH)) as this is the commonest technique for IMN RT in the UK and can be carried out quickly to ensure an efficient patient pathway.
- 5. Ability to provide written informed consent to participate in PARABLE

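### The loco-regional recurrence definition omits the chest wall, although mastectomy patients are eligible and the chest wall is irradiated

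*Protocol*

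**What the plan says.** Section 14.3.2.6 measures loco-regional tumour control as time from randomisation to loco-regional recurrence, which it spells out as "recurrence (or new primary) in ipsilateral breast or regional lymph nodes". Patients who die first are censored, and the location of a loco-regional recurrence is also said to be of interest.

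The same section defines disease-free survival by "any recurrence (local, regional or distant), contralateral breast cancer or death from breast cancer", with this censoring rule: "Patients will be censored at time of non-breast cancer death prior to recurrence or contralateral breast cancer". It then adds: "Overall survival is defined as time from randomisation to death from any cause".

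On the population, section 5.3 accepts mastectomy with axillary surgery as one of the permitted surgical routes. Its radiotherapy criterion reads "Recommended to undergo RT to the breast/chest wall +/- axilla +/- IMN". Section 14.2 makes mastectomy one of three levels of the surgery balancing factor and also balances on breast reconstruction.

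The late toxicity endpoint in section 14.3.2.3 uses a fuller list of sites: "Skin, breast / chest wall / reconstructed breast, rib and shoulder late toxicity will be assessed by clinicians".

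**The concern.** The site list that defines a loco-regional event follows an i.e., so it reads as complete rather than as examples. It fits a patient who still has a breast. It does not fit a patient after mastectomy without reconstruction, who has no ipsilateral breast and whose local target is the chest wall. For her, only a nodal recurrence clearly meets the definition.

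Cancer outcomes are a stated secondary objective (section 2.3). Section 1.1.4 argues that they will be maintained or improved with protons because target coverage is better, and section 1.1.5 notes that proton plans are more sensitive to changes in anatomy. A recurrence inside the treated chest wall bears directly on that argument, and the endpoint as worded would leave it out. There is also a risk of inconsistent coding: some staff would count a chest-wall relapse out of habit, and others would follow the text.

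**Working it through.** No figure in the protocol depends on this definition, so the check is mainly a comparison of texts.

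**Step 1. Does breast include the chest wall in this protocol?** Section 5.3 writes breast and chest wall as alternatives for the radiotherapy target. Section 14.3.2.3 lists breast, chest wall and reconstructed breast as separate items. The protocol's own usage therefore does not let breast stand for chest wall.

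**Step 2. How would one event be classified?** Take an isolated chest-wall recurrence after mastectomy without reconstruction.

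| Endpoint (section 14.3.2.6) | Sites or events counted | Is it an event? |
|---|---|---|
| Loco-regional tumour control | Ipsilateral breast, regional lymph nodes | No, read literally |
| Disease-free survival | Any local, regional or distant recurrence, contralateral breast cancer, breast cancer death | Yes, as a local recurrence on its ordinary meaning |

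A failure in the treated volume would thus be local for one endpoint and not loco-regional for its neighbour. In the loco-regional analysis the patient would stay at risk. She would become an event only if a nodal recurrence followed, and then at a later date.

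**Step 3. Direction.** Leaving out events can only leave the control rate unchanged or raise it. Type of surgery is balanced by minimisation, so mastectomy patients should be spread evenly and both arms would be affected. If chest-wall recurrence did differ by arm, this endpoint would not show it.

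**Step 4. Scale, for illustration only.** Both rates below are assumptions and do not come from the protocol.

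Events left out = 192 × mastectomy share × 5-year chest-wall recurrence risk.

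- Low: 192 × 0.30 × 0.02 = 1.2
- Middle: 192 × 0.50 × 0.02 = 1.9, and 192 × 0.50 × 0.05 = 4.8
- High: 192 × 0.70 × 0.05 = 6.7

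That is about 1 to 7 events, or 0.6% (0.30 × 0.02) to 3.5% (0.70 × 0.05) of all patients. These are upper figures within each scenario, because they treat every chest-wall recurrence as isolated and apply the literal reading to reconstructed patients too.

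**Step 5. Does anything else depend on this definition?** The power statements in section 14.1 rest on 2-year breast symptoms, mean heart dose and the mechanistic outcomes. None uses loco-regional control.

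**The case against.** The case for leaving the text alone is that the practical effect is small. Section 14.4 makes recurrence and survival analyses primarily descriptive because events are rare, and section 1.1.4 says local relapse could not feasibly be tested. A chest-wall relapse is not lost to the trial: section 10.6 requires relapse information in the eCRF, and disease-free survival counts it. Loco-regional control is not the only check on target coverage either, since section 14.3.3.3 compares planned with accumulated dose in target tissues and section 12 provides radiotherapy quality assurance. For reconstructed patients, ipsilateral breast can arguably be applied. All of this stands, and it limits the importance of the point. It does not repair the definition. Nor is this a detail left to a later document: section 14.4 defers the full analysis methods to the statistical analysis plan, but section 14.3 fixes the endpoint, and a plan that added the chest wall would contradict it.

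A reader might go further and infer that disease-free survival is also wrong because it censors non-breast-cancer deaths, cardiac deaths among them. The protocol does not support calling this an error. The rule is explicit and yields a breast-cancer-specific endpoint. The censored deaths are counted in overall survival, and heart disease deaths also in the major cardiac events endpoint (section 14.3.2.3). Section 4.2 expects major cardiac events to be rare within 5 years, so a difference in these deaths by arm during follow-up is not something the protocol anticipates. Disease-free survival does not share the chest-wall gap. What remains is a preference about the label and about how competing deaths are handled.

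**Conclusion.** The point holds for the loco-regional definition. As worded, it excludes a recurrence site that is part of the treated volume for mastectomy patients, it disagrees with the disease-free survival definition in the same section, and it would make loco-regional control look better after mastectomy than it is. The protocol supplies no figure from which the size can be derived. The range of about 1 to 7 events among 192 patients rests wholly on the assumed 30% to 70% mastectomy share and 2% to 5% chest-wall recurrence risk. Where events are few and rates are reported descriptively, a few omitted events could change the figure noticeably.

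The consequence stops at one secondary endpoint. The co-primary endpoints, the sample size and the type I error rate are unaffected.

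**What to change.** In section 14.3.2.6, define loco-regional recurrence as recurrence or new primary in the ipsilateral breast, chest wall or reconstructed breast, or regional lymph nodes. This matches the site list already used for late toxicity and removes the disagreement with disease-free survival.

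The cost is one line of text. Section 10.6 already calls for clinical, histological and imaging information at relapse, and location is already of interest, so no new data collection appears necessary. The change should be made before the 2-year and 5-year analyses named in section 14.4.

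Optionally, disease-free survival could be relabelled as a breast-cancer-specific endpoint so that its name matches its censoring rule. That is a matter of clarity and not a required correction.

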14.3.3. Mechanistic endpoints

14.3.3.1 Change in median lung Hounsfield Units per Gy on CT from baseline to 2 years

Lung density will be measured on baseline versus 2-year CTs and quantified using linear regression adjusting for mean lung dose using the methodology of Underwood⁴⁶.

14.3.3.2 Correlation of RBE-weighted dose maps with radiological changes in lungs and ribs

In patients randomised to PBT, doses to lungs and ribs on RBE-weighted dose maps for the 3 selected variable and standard RBE 1.1 models will be compared with radiological changes in lungs (lung fibrosis) and ribs (rib fractures and/or increased rib density). Candidate RBE models have been selected representing a phenomenological approach (McNamara model(43)), LET-weighted dose (McMahon(42)) and a mechanistic approach (Microdosimetric-Kinetic (44)).

14.3.3.3 Mean planned versus accumulated doses to heart and target tissues

For all patients treated in PARABLE, accumulated (i.e. delivered) dose will be calculated using deformable image registration and compared with dose from the planning CT in order to calculate percentage difference in dose.

14.4. Statistical Analysis Plan

Statistical analysis plan for co-primary outcomes

Analysis of the co-primary outcomes will take place once all patients have reached the 2-year follow-up time point (or are known to have ceased follow-up). Mean heart dose and mean 2-year breast symptoms scores will each be compared between PBT and tailored photon RT using a 2-sample t-test, and 2-sided 95% confidence intervals for the mean differences calculated. Non-inferiority of PBT for patient-reported breast symptoms at 2 years will be concluded if the upper 95% confidence limit for the difference between mean breast symptoms scores is <10; a superiority test will be carried out if

non-inferiority is shown. Although the primary analysis of the co-primary outcomes will be non-stratified, consideration will also be given in the statistical analysis plan to sensitivity analyses including adjustment for balancing and other prognostic factors. Mean heart dose data should be available for all trial participants, as this will be obtained from the RT treatment plans. Missing data for the patient questionnaires can occur in terms of missing responses to individual items or entire questionnaires not returned. The EORTC quality of life scoring manual specifies approaches for dealing with missing data. If a significant proportion of patients are not evaluable for 2-year patient-reported breast symptoms, missing data patterns will be assessed, e.g. by comparing characteristics of patients with and without 2-year questionnaires. If there appear to be differences between evaluable/non-evaluable patients, a sensitivity analysis for the co-primary patient-reported outcome assuming different missing data patterns may be performed.

Statistical analysis plan for secondary outcomes

Analyses of dosimetry outcomes (mean heart, lung and contralateral breast doses) will be done once all patients have completed their RT/PBT treatment. Analysis of mean lung and contralateral breast doses will use the same methods as described for mean heart dose.

Acute toxicity data will be analysed once all patients have reached 6 months after RT/PBT. Key time points for analysis of the other secondary outcomes including late toxicities and disease-related outcomes will be at 2 and 5 years.

Analyses of toxicity data will follow methods established in previous breast RT trials. Frequencies of early and late toxicities will be summarised at each time point and compared between treatment groups at specific time points using chi-squared test or Fisher's exact test as appropriate. Longitudinal models (e.g. generalised estimating equations) including all assessments over follow-up, and survival analyses of time to first moderate/marked adverse effect will be carried out with comparisons between treatment groups, and adjusting for balancing and other prognostic factors where appropriate. Event rates at key time points will be reported, with 95% confidence intervals.

Analyses of compliance (receipt of allocated intervention, delays and re-plans) will be largely descriptive, with proportions presented according to trial arm, along with 95% confidence intervals where appropriate.

Analyses of disease-related recurrence and survival outcomes will also be primarily descriptive due to rarity of events, which would likely preclude formal statistical comparisons.

Statistical analysis plan for mechanistic outcomes

Mechanistic outcomes will be analysed once all evaluable patients have reached 2 years' follow-up. Pre and post treatment median lung Hounsfield Units per Gy on CT will be compared between PBT and RT using the methodology of Underwood(41) and quantified using linear regression adjusting for mean lung dose. Candidate RBE models have been selected representing phenomenological approaches (McNamara model(43)) as well as different mechanistic approaches (McMahon(42) and Microdosimetric-Kinetic model(44)). Dose distributions incorporating each of the proposed RBE models will be calculated and associations with lung fibrosis and rib fractures assessed using multivariable logistic regression as per standard dose-volume/outcome modelling methodology. For

the comparison of planned and delivered dose to target and normal tissues, delivered dose will be calculated using deformable image registration and compared with dose from the planning CT in order to calculate percentage difference in dose. Non-inferiority of PBT compared with RT in terms of percentage difference between planned and accumulated dose will be tested using a t-test.

Analysis sets and subgroup analyses

All analyses will be on an intention to treat basis, including patients in the group to which they were randomised. Since protocol deviations may bias tests of non-inferiority hypotheses a sensitivity analysis of the co-primary patient-reported outcome will be done using the per protocol population excluding major treatment deviations; non-compliance will be carefully monitored during the trial.

The trial is not powered for formal subgroup analyses. However exploratory analyses will investigate differences between the treatment groups according to clinical groups including the balancing factors. Descriptive analyses will check for any differences between RT centres in terms of patient or treatment characteristics, or outcomes.

Full details of analysis methods will be specified in a Statistical Analysis Plan in accordance with ICR-CTSU Standard Operating Procedures.

